#### 2) Data Handling

Data will be analyzed as observed without imputing missing data. The cancer treatment history will refer to non-small-cell lung cancer.

The time from diagnosis date of primary disease to first dose date of the investigational product will be calculated using the following formula.

- Time from diagnosis date of primary disease to first dose date of the investigational product (days) = (the first dose date of investigational product) – (the diagnosis date of primary disease) + 1

### 8.3 Analysis Methods and Classification

1) For the background factors shown in 1) under Section [8.2 Analysis Items and Data Handling](#), the summary statistics and frequency distribution of each category will be calculated.

The ordinal scale classification and continuous quantity classification will be decided by clinical significance or dividing the sample size into three, four, or five nearly equal parts etc.

The level of measurement will be as shown below.

Item	Classification	Analysis method
Sex	Male or female	Proportion by category
Age	<65 , 65 - <75, $\geq$ 75	Summary statistics and proportion by category
Height	<160.0, 160.0-<170.0, $\geq$ 170.0	Summary statistics and proportion by category
Weight	<55.0, 55.0-<65.0, $\geq$ 65.0	Summary statistics and proportion by category
BMI	<18.5 ,18.5-<25.0, $\geq$ 25.0	Summary statistics and proportion by category
Time from diagnosis date of primary disease to first dose date of the investigational product	<180, 181-<360, $\geq$ 361	Summary statistics and proportion by category
Performance Status (ECOG)	0, 1	Proportion by category
Smoking history	Non-Smoker, Smoker or Ex-Smoker	Proportion by category
Drinking history	Non-Drinker, Drinker or Ex-Drinker	Proportion by category
Histologic type	Squamous cell carcinoma, Adenocarcinoma, Large cell carcinoma or Other	Proportion by category
Location of Initial Occurrence	LUL, LLL, RUL, RML, RLL, Unknown, Other	Proportion by category
TNM classification (T)	X, 0, is, 1a, 1b, 2a, 2b, 3, 4, Other	Proportion by category
TNM classification (N)	X, 0, 1, 2, 3, Other	Proportion by category
TNM classification (M)	X, 0, 1a, 1b, Other	Proportion by category
Metastatic Lesion	Lung(LUL, LLL, RUL, RML, RLL, Unknown, Other), Lymph Node, Liver, Bone, Brain or Other, No	Proportion by category
Stage	IIIB, IV, Recurrence, Unknown, Other	Proportion by category
Past Medical History	Yes, No	Proportion by category
Concurrent diseases	Yes, No	Proportion by category
NSCLC treatment History (Surgery)	Yes, No	Proportion by category
NSCLC treatment History (Radiotherapy)	Yes, No	Proportion by category
NSCLC treatment History (Medication)	Yes, No	Proportion by category
NSCLC treatment History (Others)	Yes, No	Proportion by category
NSCLC treatment History (Number of treatment regimens)	1, 2	Proportion by category

The analysis results will be summarized by squamous NSCLC and non-squamous NSCLC separately and totality.

2) NSCLC treatment history (medication) will be summarized. Agents and medication will be reported using the generic name.

## **9 EFFICACY EVALUATION**

### **9.1 Primary Efficacy Analysis**

#### **9.1.1 Objective**

To confirm the efficacy of ONO-4538 in stage IIIB/IV or recurrent NSCLC unsuited to radical radiotherapy and resistant to a platinum-based chemotherapeutic regimen using the response rate assessed by the central imaging analysis facility (centrally assessed) as the primary efficacy endpoint.

#### **9.1.2 Analysis Set**

Analysis will be performed in FAS.

#### **9.1.3 Analysis Items and Data Handling**

##### **1) Analysis Items**

Response rate (centrally assessed).

##### **2) Data Handling**

The response rate (centrally assessed) is defined as the number of subjects whose confirmed best overall response determined by the central imaging analysis facility (RECIST guideline version 1.1) is a CR or PR divided by the number of FAS. The subject whose confirmed best overall response is missed will be defined as the non-responder.

#### **9.1.4 Analysis Methods**

Response rate (centrally assessed) and its 95% confidence interval (Wilson) will be calculated. The analysis results will be summarized by squamous NSCLC and non-squamous NSCLC separately and totality.

### **9.2 Secondary Efficacy Analysis**

#### **9.2.1 Objective**

To perform the exploratory analyses in the endpoints other than the primary endpoint and evaluate the efficacy of investigational product from various viewpoints

#### **9.2.2 Analysis Set**

Analysis will be performed in FAS.

### **9.2.3 Analysis Items and Data Handling**

#### **1) Analysis Items**

- (1) Response rate (investigator-assessed)
- (2) Overall survival
- (3) Progression-free survival (centrally assessed and investigator-assessed)
- (4) Time to progression (centrally assessed)
- (5) Duration of response (centrally assessed)
- (6) Time to response (centrally assessed)
- (7) Best overall response (centrally assessed and investigator-assessed)
- (8) Percent change in tumor diameter of target lesion (investigator-assessed)

#### **2) Data Handling**

Overall response and best overall response will be defined as diagnostic imaging results evaluated in compliance with RECIST guideline version 1.1 and will not include clinical deterioration. Evaluable diagnostic imaging will be defined as diagnostic imaging which provides assessment other than NE.

- (1) The response rate (investigator-assessed) is defined as the number of subjects whose confirmed best overall response determined by the study site investigator is a CR or PR divided by the number of FAS. The subject whose objective response is missed will be defined as the non-responder.
- (2) Overall survival will be calculated using the following formula.

➤ Overall survival (days) = (the date of death due to any cause) - (the first dose date of investigational product) + 1

A subject who has not died will be censored at last known date alive.

- (3) Progression-free survival (centrally assessed and investigator-assessed) will be calculated using the following formula.

➤ Progression free survival (days) = (the earlier date of the first documented PD or death due to any cause) - (the first dose date of investigational product) + 1

Clinical deterioration will not be included as an event in progression-free survival when progression-free survival is evaluated based on diagnostic imaging results interpreted by the image central analysis laboratory; it will be included, however, when progression-free survival is evaluated based on diagnostic imaging results interpreted by a physician at the trial site.

In addition, event/censoring assessment will be performed according to [Table 9-1](#).

Table 9-1 Criteria for event/censoring assessment in progression-free survival (centrally assessed and investigator-assessed)

Status	Event or censoring date	Result
Subjects for whom diagnostic imaging was missed at baseline.	Date of starting the study treatment	Censoring
Subjects for whom evaluable diagnostic imaging has not been performed and who are alive	Date of starting the study treatment	Censoring
Subjects who received subsequent anti-cancer therapy for non-small-cell lung cancer before he/she died or were assessed as having PD	Date when the last evaluable diagnostic imaging was performed before starting subsequent anti-cancer therapy for non-small-cell lung cancer	Censoring
Subjects for whom the outcome follow-up for non-small-cell lung cancer was ended before death or assessment as PD	Date when the last evaluable diagnostic imaging was performed before the end of the outcome follow-up for non-small-cell lung cancer	Censoring
Subjects who are alive and have not been assessed as having PD	Date when the last evaluable diagnostic imaging was performed	Censoring
Subjects who died or have been assessed as having PD	Date of death or date when the first diagnostic imaging to provide assessment as PD was performed, whichever comes first	Event
Subjects who died before initial evaluable diagnostic imaging	Date of death	Event

(4) Time to progression (centrally assessed) will be calculated based on assessment by the central imaging analysis facility with the following formula:

- Time to progression (days) = (the date of the first documented PD) - (the first dose date of investigational product) + 1

In addition, event/censoring assessment will be performed according to [Table 9-2](#).

Table 9-2 Criteria for aggravation/censoring assessment in time to progression (centrally assessed and investigator-assessed)

Status	Event or censoring date	Result
Subjects for whom diagnostic imaging was missed at baseline.	Date of start of the study treatment	Censoring
Subjects for whom evaluable diagnostic imaging has not been performed	Date of start of the study treatment	Censoring
Subjects who received subsequent anti-cancer therapy for non-small-cell lung cancer before assessment as PD	Date when the last evaluable diagnostic imaging was performed before starting subsequent anti-cancer therapy for non-small-cell lung cancer	Censoring

Status	Event or censoring date	Result
Subjects for whom the outcome follow-up for non-small-cell lung cancer was ended before death or assessment as PD	Date when the last evaluable diagnostic imaging was performed before the end of the outcome follow-up for non-small-cell lung cancer	Censoring
Subjects who have not been assessed as having PD	Date when the last evaluable diagnostic imaging was performed	Censoring
Subjects who have been assessed as having PD	Date when the first diagnostic imaging to provide assessment as PD was performed	Event

(5) Duration of response (centrally assessed) will be calculated based on assessment by the central imaging analysis facility with the following formula:

- Duration of response (days) = (the date of the first documented PD or death due to any cause after response is confirmed) - (the date of the first confirmed CR or PR) + 1

Subjects without documented PD and who did not die will be censored at the last evaluable tumor assessment. Subjects who are not evaluated a confirmed CR or PR at any time during the study will be excluded from this analysis.

(6) Time to response (centrally assessed) will be calculated based on assessment by the central imaging analysis facility with the following formula:

- Time to response (days) = (the date of the first confirmed CR or PR) - (the first dose date of investigational product) + 1

Subjects who are not evaluated confirmed CR or PR at any time during the study will be excluded from this analysis.

(7) Percent change in tumor diameter of target lesion (investigator-assessed)

With regard to the tumor diameter (sum of the longest diameters of target lesions) evaluated by a investigator at the trial site according to RECIST guideline version 1.1, the best percent change and percent change at each time point will be calculated using the following formulas.

The calculation of the best percent change will not include the longest diameters of target lesions measured after the overall response is assessed as PD; any subsequent anti-cancer therapy is performed for non-small-cell lung cancer; or subsequent anti-cancer therapy follow-up is ended. The percent change at each time point will be calculated also after the overall response is assessed as PD but will not after any subsequent anti-cancer therapy for non-small-cell lung cancer or the outcome follow-up is ended.

$$\text{➤ Best percent change} = \frac{\text{Smallest tumor diameter after first dose} - \text{Baseline tumor diameter}}{\text{Baseline tumor diameter}} \times 100$$

$$\triangleright \text{Percent change} = \frac{\text{Tumor diameter at evaluation point} - \text{Baseline tumor diameter}}{\text{Baseline tumor diameter}} \times 100$$

Subjects without measurable lesion or without any tumor assessment after first dose will be excluded from this analysis.

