### **3.6 Investigational Product Discontinuation Criteria**

Subjects satisfying any of the following criteria in the treatment phase will be discontinued the investigational product and proceed to the follow-up phase.

1. The development of PD is identified by the principal or sub investigator according to the RECIST guideline (version 1.1).
2. A worsening of clinical symptoms attributed to disease progression occurs.
3. The subject develops Grade 2 or higher interstitial lung disease, regardless of the causal relationship to the investigational product.
4. Grade 2 or greater eye pain, or visual acuity reduced occurs whose causal relationship with the investigational product cannot be ruled out and does not improve to Grade 1 severity with local treatment.
5. Grade 3 or greater bronchospasm, hypersensitivity reaction, infusion reaction (e.g., pyrexia, chills, nausea, pain, headache, cough, pruritus, rash) or uveitis occurs whose causal relationship with the investigational product cannot be ruled out.
6. An adverse event or other events delay the administration of the investigational product by more than 6 weeks.
7. The investigator or sub investigator otherwise determines that continuing to administer the investigational product is inappropriate due to an efficacy- or safety-related reason.

Even when Criterion 1 is applicable, investigational product treatment may be continued if it is determined through consultation with the sponsor that no worsening of clinical symptoms attributable to disease progression occurs, continued treatment is expected to provide a clinical benefit, and the investigational product can continue to be safely administered. If the investigational product is to be continued, the subject should first be consulted about his or her willingness to continue receiving treatment, and this process should be documented in the medical records. Laboratory tests will be frequently repeated and other measures taken to adequately ensure subject safety. Any subject who is found to have again developed PD according to the RECIST guideline (version 1.1) based on a point

where a decision is made to continue investigational product treatment must cease using the investigational product regardless of whether clinical symptoms have worsened or not.

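### Investigator-assessed PFS: the SAP text makes clinical deterioration an event, but the PFS formula and Table 9-1 leave it out and, read literally, censor it

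*SAP*

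**What the plan says.** SAP 9.2.3 2)(3) defines PFS once for both assessments. The formula runs from first dose to "the earlier date of the first documented PD or death due to any cause". The next paragraph separates the two versions: clinical deterioration is not an event in central PFS, but for the investigator version "it will be included, however, when progression-free survival is evaluated based on diagnostic imaging results interpreted by a physician at the trial site".

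Table 9-1 follows as an additional set of rules, headed for both assessments. It has seven rows.

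- **Two event rows.** The main one is dated "Date of death or date when the first diagnostic imaging to provide assessment as PD was performed, whichever comes first". The other covers death before any evaluable imaging.
- **Five censoring rows.** They include "Subjects who received subsequent anti-cancer therapy for non-small-cell lung cancer before he/she died or were assessed as having PD" and "Subjects who are alive and have not been assessed as having PD", both censored at a last evaluable scan. Living subjects without evaluable imaging are censored at treatment start. The other two cover end of outcome follow-up and missed baseline imaging.

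No row mentions clinical deterioration. Under SAP 9.2.4 3), investigator PFS has its own Kaplan-Meier curve, median and rates at 3, 6, 9 and 12 months.

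**The concern.** The text and the table classify the same subject in opposite ways. A living subject whose disease has worsened clinically, without a scan showing PD, is an event by the text. By the table that subject is censored before the worsening. Such subjects are removed from the risk set because they got worse, so the Kaplan-Meier assumption of non-informative censoring fails and the investigator curve is raised.

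The case can arise in practice. SAP 3.6 lists "A worsening of clinical symptoms attributed to disease progression occurs" as a reason to stop treatment, separate from RECIST PD. A subject can therefore stop on symptoms and start another therapy without imaging PD, and the subsequent-therapy row then censors that subject.

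Even a programmer who follows the text must choose an event date and decide which censoring rows it overrides. Neither is stated. SAP 9.2.4, 14, 15 and 16.2 and the protocol add no rule.

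**Working it through.** **1. Plan's own figures.** The SAP gives no PFS event count, power or expected rate. Its only design calculation (3.7.2) is for response rate. That formula gives 40.49 and 51.07, which round up to the stated 41 and 52, and PFS plays no part in it.

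**2. Text against table, with assumed days.** The text column takes the deterioration day as the event date, which is itself an assumption.

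| Subject | By the text | By Table 9-1 |
|---|---|---|
| SD Day 43, deterioration Day 60, new therapy Day 70 | Event, Day 60 | Censored, Day 43 |
| Deterioration Day 25, alive, no evaluable imaging | Event, Day 25 | Censored, Day 1 |
| SD Day 43, deterioration Day 60, no new therapy, death Day 120 | Event, Day 60 | Event, Day 120 |

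The first two subjects change status. The third changes only in date.

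**3. Inputs for size.**
- Scans every 42 days (protocol Table 4-2, footnote 13).
- One month = 30.4375 days (SAP 9.2.4).
- 96 treated subjects (SAP 14.4). The FAS is the treated set (SAP 4.1).
- Assumed: exponential progression with median M = 2.3 or 3.1 months. These are the docetaxel figures in SAP 1, used as a stand-in because no PFS for ONO-4538 is given.
- Assumed: a share f = 2 to 20% of progressions is clinical only, meaning that neither imaging PD nor an untreated death follows. The documents give no value for f.

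**4. Text governs, only the date is open.** For an assumed 14-day difference, the shift at time t is f × [S(t − 14 days) − S(t)], with S(t) = 0.5^(t/M).
- 3 months: 0.465 − 0.405 = 0.060 (M = 2.3) and 0.567 − 0.511 = 0.055 (M = 3.1). With f = 2 to 20%, the shift is 0.11 to 1.2 points.
- 6 months: 0.188 − 0.164 = 0.024 and 0.290 − 0.261 = 0.028. The shift is 0.05 to 0.57 points.

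**5. Table alone is programmed.** This is a simulation with 2,000,000 subjects per scenario. Under the text, clinical-only progressors are events at the true time. Under the table, they are censored at the previous scan, or Day 1 if none. All others are events at the next scan. The 6-month PFS (%) is shown below, with differences taken before rounding.

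| f (about n of 96) | M = 2.3: text → table | Points | M = 3.1: text → table | Points |
|---|---|---|---|---|
| 2% (2) | 18.9 → 19.4 | 0.6 | 29.1 → 29.7 | 0.7 |
| 5% (5) | 18.8 → 20.3 | 1.5 | 29.0 → 30.7 | 1.7 |
| 10% (10) | 18.7 → 21.7 | 3.1 | 28.8 → 32.4 | 3.6 |
| 20% (19) | 18.4 → 25.1 | 6.7 | 28.5 → 36.2 | 7.7 |

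The median, which steps with the scan dates, moves in only one of these eight scenarios (M = 2.3, f = 20%: 2.8 to 4.2 months).

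**6. Sampling error at 6 months.** sqrt(0.187 × 0.813/96) = 4.0 points and sqrt(0.288 × 0.712/96) = 4.6 points. At the planned 52 and 41 subjects per histology, the same formula gives 5.4 to 7.1 points.

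**The case against.** The strongest reply is that the text settles the matter. It states the status for each assessor just before the table, and the table is introduced as an addition. The exclusion of clinical deterioration at the head of 9.2.3 2) concerns overall and best overall response, so documented PD in the PFS formula could include clinical progression recorded by the investigator. Only a date and a rank would then be missing, worth at most about 1.2 points under the stated assumptions.

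Much of this stands. The text is the more natural rule, and a reader might wrongly infer that investigator PFS is inflated by up to 7.7 points. That needs the table to override an explicit sentence and a 20% share that nothing in the documents supports. Imaging is scheduled at the end of treatment and 28 days after the final dose, and afterwards where possible for subjects still in CR, PR or SD (SAP Table 3-3). This should reduce the clinical-only share. A later death without new therapy remains an event under either rule.

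The wider reading of documented PD does not remove the conflict. The table's event row dates PD by the first imaging that shows it, and no other section supplies a date or rank.

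A reader might also infer that the data review of 96 subjects used the wrong rule. The SAP says only that items were handled as already defined (14.3), and a plan is not expected to report more. Nothing shows an error was made.

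**Conclusion.** The contradiction is real and lies in current SAP text. Two stated rules give opposite results for a living subject with clinical deterioration and no imaging PD, and the table's rule censors informatively in a direction that raises the investigator curve.

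The likely size is small: about 0.05 to 1.2 points at 3 and 6 months if the text governs. The range of 0.6 to 7.7 points at 6 months is a worst case for table-only programming. Both ranges rest on the assumed share, exponential progression and the docetaxel medians; the first also assumes a 14-day difference. Confidence is high in the textual conflict, and much lower in any particular size.

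Investigator PFS is secondary, the SAP calls these analyses exploratory (9.2.1), and no test is planned (12.2). The primary response rate, central PFS and the sample size are unaffected. Severity: minor.

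**What to change.** Make Table 9-1 and the formula agree with the text.

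- **Add one row, for investigator-assessed PFS only.** Clinical deterioration attributed to disease progression, recorded by the investigator before imaging PD, death or subsequent NSCLC therapy, is an event on one pre-specified date, for example the date the investigator determined it.
- **State its rank.** It takes precedence over the rows for no evaluable imaging, subsequent therapy, end of follow-up and alive without PD. Its order against the row "Subjects for whom diagnostic imaging was missed at baseline" should also be stated. That row should be nearly empty, since inclusion criterion 5 requires imaging within 14 days before enrolment.
- **Add the matching term to the PFS formula**, for the investigator version only.
- **Do not define the event by discontinuation criterion 2 alone.** That criterion applies only in the treatment phase and would miss deterioration during follow-up, which the text does not exclude.
- **Confirm that the eCRF holds the date.** SAP 6.2 lists the reason for ending treatment but no deterioration date.
- **Report how many subjects the row reclassifies**, so that the actual effect can be seen.

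The cost is one table row, one precedence sentence, one formula term and a little reprogramming, provided the date was collected. This keeps the sponsor's stated definition. Deleting the sentence would also remove the conflict, but would change that definition.

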#### 9.2.4 Analysis Methods

With regard to the analysis items shown in 1) under Section 9.1.3 Analysis Items and Data Handling, the following analyses will be performed. The analysis results will be summarized by squamous NSCLC and non-squamous NSCLC separately and totality.

- 1) Response rate (investigator-assessed) and its 95% confidence interval (Wilson) will be calculated.
- 2) The following analyses will be performed for overall survival and time to progression.

A Kaplan-Meier curve will be plotted for each analysis variable. The median and its 95% confidence interval and overall survival rates at 6, 12, 18 and 24 months and its 95% confidence interval will be estimated by Kaplan-Meier method. 6, 12, 18 and 24 months will be calculated assuming 30.4375 days for one month.

- 3) The following analyses will be performed for progression free survival.

Two Kaplan-Meier curves will be plotted based on the interpretation by the image central analysis laboratory and that by an investigator at the trial site. The median progression free survival, its 95% confidence interval and progression free survival rates at 3, 6, 9 and 12 months and its 95% confidence interval will be estimated by Kaplan-Meier method. 3, 6, 9 and 12 months will be calculated assuming 30.4375 days for one month.

- 4) Summary statistics will be calculated for duration of response. The median and its 95% confidence interval and duration of response rates at 6 and 12 months and its 95% confidence interval will be estimated by Kaplan-Meier method. 6 and 12 months will be calculated assuming 30.4375 days for one month.
- 5) Summary statistics will be calculated for time to response. The median and its 95% confidence interval will be estimated by Kaplan-Meier method.
- 6) For best overall response, the percentages of CR, PR, SD, PD, and NE will be calculated based on the interpretation by the image central analysis laboratory and that by an investigator at the trial site. In addition, the 95% confidence intervals (Wilson) will be calculated in CR, PR and SD.
- 7) Waterfall plot will be displayed for best percent change in tumor diameter of target lesion. In addition, a plot of individual subjects' percent change in tumor diameter of target lesion will be displayed at individual time point.

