#### **3.7.2 Rationale for Number of Subjects**

The objective of the study is to investigate the efficacy of ONO-4538 in patients with stage IIIB/IV or recurrent NSCLC unsuited to radical radiotherapy using centrally assessed response rates as the primary endpoint. The sample size for each histology is calculated in order to confirm anti-tumor response of ONO-4538 in Korean population.

From efficacy data of non-Korean phase I multiple-dose study (CA209003) as of March 18, 2013 ([Table 3-4](#)), the expected response rate for ONO-4538 in patients with squamous NSCLC was set at 23.1% because responses of 22% (4/18) and 24% (5/21) were achieved in patients with squamous NSCLC in the 3 and 10 mg/kg group, respectively. Similarly, the expected response rate for ONO-4538 in patients with non-squamous NSCLC was set at 21.4% because responses of 26% (5/19) and 19% (7/37) were achieved in patients with non-squamous NSCLC in the 3 and 10 mg/kg group, respectively. The threshold response rate (the null hypothesis) was set at 8.8% because the response rate of docetaxel, which was selected as a comparator in non-Korean Phase III studies (CA209017, CA209057), was 8.8% in the phase III trial in patients with NSCLC. Under the assumption of the threshold response rate of 8.8% and the expected response rate of 23.1% and 21.4% for patients with squamous and non-squamous NSCLC respectively, 41 subjects for squamous and 52 subjects for non-squamous will provide a statistical power of at least 80% in a binomial test (normal approximation) with an one-sided significance level of 2.5% (two-sided significance level of 5.0%). The sample sizes (i.e., 41 subjects with squamous NSCLC and 52 subjects with non-squamous NSCLC) were calculated using the formula as follows.

$$N = \left( \frac{z_{1-\alpha} \sqrt{p_0(1-p_0)} + z_{1-\beta} \sqrt{p_1(1-p_1)}}{p_1 - p_0} \right)^2$$

*N*: the number of subjects

*p*0: threshold response rate

*p*1: expected response rate

$z_{1-\alpha}$ :  $(1 - \alpha) \cdot 100$  quantile of the standard normal distribution

$z_{1-\beta}$ :  $(1 - \beta) \cdot 100$  quantile of the standard normal distribution

$\alpha$ : one-sided significance level

$1 - \beta$ : statistical power

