## 12 GENERAL PRESENTATION OF SUMMARIES AND ANALYSES

### 12.1 Summary Statistics

As summary statistics, mean, standard deviation, median, maximum, and minimum will be calculated unless otherwise noted.

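### The SAP orders ordinary summary statistics for duration of response, a censored variable, and gives no rule for censored values; the mean and SD are biased downward unless follow-up is long

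*SAP*

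**What the plan says.** SAP 9.2.3, Data Handling item (5), runs duration of response from the first confirmed CR or PR to "the date of the first documented PD or death due to any cause after response is confirmed". It then adds: "Subjects without documented PD and who did not die will be censored at the last evaluable tumor assessment". The variable is therefore right-censored.

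SAP 9.2.4 item 4) gives two separate instructions for it. The first is "Summary statistics will be calculated for duration of response". The second asks for a median with its confidence interval, and "duration of response rates at 6 and 12 months and its 95% confidence interval will be estimated by Kaplan-Meier method".

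SAP 12.1 fixes what the first instruction means: "As summary statistics, mean, standard deviation, median, maximum, and minimum will be calculated unless otherwise noted".

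Two comparisons within the SAP help:

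- For overall survival, time to progression and progression-free survival (9.2.4 items 2 and 3), only Kaplan-Meier estimates are ordered. Duration of response is the only censored efficacy endpoint that also gets ordinary summary statistics.
- Time to response (9.2.4 item 5) has the same wording, but there it is harmless: "Subjects who are not evaluated confirmed CR or PR at any time during the study will be excluded from this analysis". Everyone analysed has an observed time, so nothing is censored.

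**The concern.** A mean and SD need completed durations. For a responder still in response at the cut-off, only a lower bound is known. The SAP does not say what to do with that bound, and a programmer has two obvious choices: use the censored time as if the response had ended, or leave the responder out. Both pull the mean and SD down, and the responders they misrepresent are the ones doing best.

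Two further items in the list are exposed. A raw median, if tabulated, would stand beside the Kaplan-Meier median and could disagree with it. The maximum may be a response that had not ended, and nothing requires it to be marked.

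Duration of response is the durability result that readers set beside a response-rate primary endpoint. At an early cut-off, a table giving a mean well below the true one would understate durability.

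**Working it through.** **Number of responders.** SAP 3.7.2 gives a threshold of 8.8%, "the expected response rate of 23.1% and 21.4% for patients with squamous and non-squamous NSCLC respectively", one-sided 2.5% and power of at least 80%. Its formula reproduces the plan's sizes: 40.49, rounded up to 41 (power 80.4%), and 51.07, rounded up to 52 (power 80.6%). Expected responders are 41 × 0.231 = 9.5 and 52 × 0.214 = 11.1, about 21 in all.

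**Assumptions.** The documents give no duration-of-response figure and no fixed cut-off. I assume exponential durations with median 12 months, so mean and SD are both m = 12 / ln 2 = 17.3 months, and rate λ = ln 2 / 12. Follow-up C from response is uniform between a and b months, with no censoring other than the cut-off.

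**Formulas.**

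- Censored fraction: π = (e^(−λa) − e^(−λb)) / (λ(b − a)).
- Mean, censored times counted as ended: m(1 − π).
- K = E[C·e^(−λC)] = (F(a) − F(b)) / (b − a), with F(c) = (cm + m²)e^(−λc).
- Mean, censored responders dropped: m − K / (1 − π).
- SD, counted as ended: the square root of 2m²(1 − π) − 2mK − [m(1 − π)]².
- Raw median, counted as ended: the t that solves e^(−λt)·P(C > t) = 0.5.

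**Worked case, 6 to 18 months.** π = (0.707 − 0.354) / 0.693 = 0.51. Mean counted as ended = 17.3 × 0.49 = 8.5. F(6) − F(18) = 69.2, so K = 69.2 / 12 = 5.77, and the mean with censored responders dropped = 17.3 − 5.77 / 0.49 = 5.5. SD = √(293.7 − 199.8 − 71.9) = 4.7. At t = 8.3, e^(−λt) = 0.619 and P(C > t) = 9.7 / 12 = 0.808. Their product is 0.50, so the raw median is 8.3.

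| Follow-up (months) | Censored | Mean, counted as ended | Mean, dropped | SD, counted as ended | Raw median, counted as ended | Raw median, dropped |
|---|---|---|---|---|---|---|
| 3–12 | 66% | 6.0 | 3.8 | 3.1 | 5.7 | 3.3 |
| 6–18 | 51% | 8.5 | 5.5 | 4.7 | 8.3 | 4.9 |
| 12–24 | 36% | 11.1 | 7.5 | 6.7 | 12.0 | 6.7 |
| 60–84 | 2% | 17.0 | 16.1 | 16.1 | 12.0 | 11.7 |
| True value | – | 17.3 | 17.3 | 17.3 | 12.0 | 12.0 |

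Simulation with 21 responders (4,000 runs per row) agrees with the censored fractions, the counted-as-ended means and the raw medians. It gives a Kaplan-Meier median of 12.1, 12.0 and 12.0 in rows two to four, not reached in 24%, 4% and 0% of runs. In the first row it was not reached in 59% of runs.

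The raw median behaves differently from the mean. Once every responder has been followed beyond the true median (rows three and four), counting censored times as ended leaves the median at 12.0. The mean is still short by 17.3 − 11.1 = 6.2 months in row three.

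**Small example.** Take ten durations 3, 4+, 5, 6, 6+, 7+, 8+, 9, 10+, 12+ (+ means ongoing). Counted as ended, the mean is 7.0 and the median 6.5. With ongoing responses dropped they are 5.75 and 5.5. The Kaplan-Meier median is 9. The maximum, 12, is a response that has not ended.

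**The case against.** Four points can be made for the plan.

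- A reader might infer that the SAP tells the programmer to treat ongoing responses as ended. It does not. The formula in 9.2.3 ends only at PD or death, so statistics on completed responses are just as possible. This stands. The fault is a missing rule, but neither way of filling it gives a valid mean or SD.
- A reader might also infer that the table must carry a second, wrong median. The default list in 12.1 yields to anything noted otherwise, and the next sentence of 9.2.4 item 4) assigns the median to Kaplan-Meier. That can fairly be read as replacing the raw median. This also stands. It does not remove the mean, SD or maximum.
- The early cut-offs may not apply to the current SAP. It is dated 29 July 2021, and 96 subjects had been treated by 27 February 2015 (SAP 14.4), about 77 months earlier. At that distance the raw and Kaplan-Meier medians agree. This largely stands. However, Protocol section 11 leaves the cut-off open. Imaging after discontinuation is only done where possible, which can add censoring that the table does not count. Protocol Table 4-2, note 13, schedules imaging beyond Cycle 30 (30 × 6 = 180 weeks), so the longest response could still be ongoing.
- The endpoint is secondary, SAP 9.2.1 calls these analyses exploratory, 12.2 plans no tests, and valid Kaplan-Meier estimates are already ordered. This stands and limits the severity.

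**Conclusion.** Wrong as written, and minor. Followed literally, SAP 9.2.4 item 4) yields a mean and SD for a censored variable with no rule for the censored values. Both are biased downward under either way of handling them. Whether a conflicting median would appear is open. An unflagged maximum is a risk at any cut-off.

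The size rests on assumed inputs: exponential durations with median 12 months, uniform follow-up and cut-off censoring only. On those, the mean counted as ended is about half the true value with 6 to 18 months of follow-up (8.5 against 17.3), about two thirds with 12 to 24 months (11.1), and nearly right with 60 to 84 months (17.0). With assumed medians of 6 to 18 months and 3 to 12 months of follow-up, 44% to 75% of responders are censored, and the mean is 4.9 to 6.4 months against true means of 8.7 to 26.0.

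The documents do not support a claim that the reported duration will be badly wrong at the cut-off that SAP version 3.0 points to. The primary endpoint, the sample size and the Kaplan-Meier estimates of duration of response are untouched.

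**What to change.** In SAP 9.2.4 item 4), delete the summary-statistics sentence for duration of response. In its place, by histology and in total, report:

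- the number of responders with an event and the number censored;
- the Kaplan-Meier median with its 95% confidence interval;
- the 6- and 12-month Kaplan-Meier rates with 95% confidence intervals;
- the range, with each censored value marked +.

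The second and third items are already planned. Summary statistics may stay for time to response in item 5), where nothing is censored.

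The cost is an edit to one SAP item and a simpler table. No new data are needed, and nothing changes for patients, sample size or power.
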